4.2.2.13.2 Safety Analysis Set

The analyses described in the above section 4.2.2.13.1 will be produced using the SAF for:

- savolitinib (300 mg od, 300 mg bid and 600 mg od, respectively) in combination with osimertinib in patients with EGFRm+, MET amplified/overexpressed (FISH10+ and/or IHC90+), locally advanced or metastatic NSCLC who have progressed following osimertinib
- savolitinib (300 mg od, 300 mg bid and 600 mg od, respectively) in combination with osimertinib in patients with EGFRm+, MET amplified/overexpressed (FISH5+ and/or IHC50+), locally advanced or metastatic NSCLC who have progressed following osimertinib

Details of tumour assessment and response will be listed for each patient. This listing will include information on target lesion sites, the method of assessment, diameter of target lesion, sum of diameters of target lesions, percent change from baseline, non-target lesions, new lesions, the calculated visit response and best objective response.

4.2.2.14 Supplementary Analysis based on IUO grade status

4.2.2.14.1 Supplementary Analyses of Objective Response Rate and Duration of Response

4.2.2.14.1.1 Target Population Analysis set

FISH10+ and/or IHC90+ MET status will be re-assessed retrospectively utilising IUO grade MET testing. ORR and DoR will be reproduced with CSPv7 patients identified for FISH10+ and/or IHC90+ MET status using retrospective IUO grade testing. ORR and DoR will be assessed according to primary endpoint approach (by investigator).

4.2.2.14.1.2 Subgroup Analysis

Subgroups analyses of ORR re-assessed retrospectively utilising IUO grade MET testing will be conducted on TPAS within the following subgroups (Appendix “A”):

- Race [Asian, Non-Asian]
- Sex [Male, Female]
- Age at baseline [<65 years, ≥65 years]

- T790M status in baseline plasma [T790M+, T790M-]
- C797S mutation in baseline plasma [C797S+, C797S-]
- FISH+ allocation status [Amplified, Polysomy]. Patients can be considered FISH+ by either amplification or polysomy, where amplification is considered a ratio of 'Mean MET/CEP7 RATIO' or 'CEP7/MET RATIO' ≥ 2 and polysomy where ratio < 2 . The non-FISH+ patients will be excluded. Ratio information will be provided by external vendor
- IHC+ allocation status [IHC90+, IHC90 negative (FISH10+), IHC50+, IHC50 negative (FISH5+), IHC missing/unknown (FISH+ to enter study)]
- FISH+ allocation status [FISH10+, FISH10 negative (IHC90+), FISH5+, FISH5 negative (IHC50+), FISH missing/unknown (IHC+ to enter study)]
- Overall disease classification [Metastatic, Locally advanced, Missing]
- EGFR mutation status [Exon 19 deletion, L858R]
- Known or treated brain metastases at study entry [Yes (present at baseline or not present at baseline but with known or treated history of brain metastases), No (not present at baseline and not known or treated history of brain metastases)]. This classification will be identified by an AstraZeneca medically qualified expert during the medical review process
- ECOG at baseline [0, 1, ...]
- Histological Type [Adenocarcinoma, Other].

4.2.2.14.1.3 Safety Analysis Set

FISH10+ and/or IHC90+ MET status will be re-assessed retrospectively utilising IUO grade testing. Summaries for ORR and DoR will also be re-produced utilising the IUO grade status on SAF for:

- savolitinib (300 mg od, 300 mg bid and 600 mg od, respectively) in combination with osimertinib in patients with EGFRm+, MET amplified/overexpressed (FISH10+ and/or IHC90+), locally advanced or metastatic NSCLC who have progressed following osimertinib

4.2.2.14.1.4 Contribution of Component Analysis Set

Finally, summaries for ORR will be re-produced using the CAS using retrospective IUO grade MET status for:

- 300 mg bid (savolitinib) + osimertinib
- 300 mg bid (savolitinib) + placebo.

4.2.2.14.2 Supplementary Analyses of Progression Free Survival

4.2.2.14.2.1 Target Population Analysis Set

FISH10+ and/or IHC90+ MET status will be re-assessed retrospectively utilising IUO grade MET testing. PFS will be reproduced with CSPv7 patients identified for FISH10+ and/or IHC90+ MET status using retrospective IUO grade testing. PFS will be assessed according to primary endpoint approach (by investigator).

4.2.2.14.2.2 Safety Analysis Set

Summaries for PFS will also be re-produced utilising the IUO grade status on SAF for:

- savolitinib (300 mg od, 300 mg bid and 600 mg od, respectively) in combination with osimertinib in patients with EGFRm+, MET amplified/overexpressed (FISH10+ and/or IHC90+), locally advanced or metastatic NSCLC who have progressed following osimertinib

4.2.3 Safety and Tolerability Data

Unless otherwise stated, analysis of safety data will be based on SAF for patients dosed under all CSP versions as follows:

- savolitinib (300 mg od, 300 mg bid and 600 mg od, respectively) in combination with osimertinib in patients with EGFRm+, MET amplified/overexpressed (FISH10+ and/or IHC90+), locally advanced or metastatic NSCLC who have progressed following osimertinib
- savolitinib (300 mg od, 300 mg bid and 600 mg od, respectively) in combination with osimertinib in patients with EGFRm+, MET amplified/overexpressed (FISH5+ and/or IHC50+), locally advanced or metastatic NSCLC who have progressed following osimertinib
- savolitinib in monotherapy (i.e., 300 mg bid + placebo)

Dedicated analysis for patients randomised under CSP version 7.0 may be performed.

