1.3 Schema

Figure 1 Study design

^a IHC50+: ≥50% of tumour cells staining at strong 3+ intensity; FISH5: ≥5 MET gene copies or MET:CEP7 ratio ≥2 as determined by central testing. Under CSP versions 1-5, MET amplification as determined by pre-existing local NGS were also allowed. Under CSP version 6, only MET FISH5+ status as determined by central testing was allowed for eligibility.

^b IHC90+: >=90% of tumour cells staining at strong 3+ intensity; FISH10: ≥10 MET gene copies; as determined by central testing.

^c A futility analysis for the savolitinib + placebo arm is planned after ~~CCl~~ patients have been randomised under CSP version 7.0 and have had an opportunity to have 2 post-baseline scans. If the decision is made that treatment with savolitinib + placebo is futile, further enrolment into the savolitinib + placebo arm will be stopped.

1L First-line; bid; Twice daily; CSP Clinical Study Protocol; ECOG Eastern Cooperative Oncology Group; EGFRm+ Epidermal growth factor receptor mutation positive; EGFR-TKI EGFR-tyrosine kinase inhibitor; FISH Fluorescence in situ hybridisation; IHC Immunohistochemistry; MET Mesenchymal epithelial transition factor; MET/CEP7 Mean MET per cell and chromosome 7 centromere ratio; NSCLC Non-small cell lung cancer; od once daily; PD Progressive disease; RECIST Response Evaluation Criteria in Solid Tumours.

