9.3 Populations for analyses

For purposes of analysis, the following populations are defined:

Population	Description
Target Population Analysis Set (TPAS)	All patients assigned to savolitinib 300 mg bid + osimertinib who have FISH10+ and/or IHC90+ status, have progressed following 1L osimertinib, and have taken ≥ 1 dose of either study drug.
Contribution of Components Analysis Set (CAS)	All patients randomised under CSP version 7.0 with treatment groups assigned in accordance with the randomisation, regardless of the treatment actually received.
Safety Analysis Set (SAF)	All enrolled patients who take ≥ 1 dose of either study drug.
PK population	All patients who receive at least 1 dose of savolitinib or osimertinib as per the protocol, for whom any post-dose PK data are available and do not violate or deviate from the protocol in ways that would significantly affect the PK analyses will be included in the PK analysis set.
Evaluable for Response	Dosed patients who have measurable disease at baseline.
Evaluable for Response 2	Dosed patients with measurable disease at baseline who have had the opportunity for 2 on-treatment RECIST scans.
Safety Analysis Set 2 (SAF2)	All enrolled patients who take ≥ 1 dose of either study drug who have had the opportunity to be treated for 6 weeks.

CSP Clinical study protocol; FISH Fluorescence in situ hybridisation; IHC immunohistochemistry; PK Pharmacokinetic(s); RECIST Response Evaluation Criteria in Solid Tumours.

Patients will be assigned to each of these populations and to the diagnostic populations (centrally confirmed by FISH [FISH5+, FISH10+] and centrally confirmed by IHC [IHC50+, IHC90+]), prior to any analyses being performed.

The Target Population Analysis Set (TPAS) will be used as the population for reporting efficacy and to summarise baseline characteristics for patients dosed with savolitinib 300 mg bid + osimertinib who are FISH10+ and/or IHC90+ and have progressed following treatment with 1L osimertinib (primary endpoint population).

The Contribution of Components Analysis Set (CAS) will be used as the population for reporting efficacy and to summarise baseline characteristics for patients randomised under CSP version 7.0.

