The SAF will be used for reporting efficacy of savolitinib 300 mg od + osimertinib in FISH5+ and/or IHC50+ patients (primary endpoint population). The SAF will also be used as the population for reporting efficacy and to summarise baseline characteristics for patients dosed prior to CSP version 7.0. The Safety Analysis Set (SAF) will be used as the population for reporting safety for patients dosed under all CSP versions.

For the PK population, where a protocol deviation impacts only part of a patient's data, the affected portion of the patient's PK data will be excluded from PK analysis and summary statistics, and the remaining valid data will be utilised.

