9.4.4 Safety analyses

The SAF will be used as the population for reporting safety for patients dosed under all CSP versions (see Section 9.3 for analysis set definitions).

Safety and tolerability will be assessed in terms of AEs, deaths, laboratory data, vital signs, ECG data and ECOG performance status.

The Medical Dictionary for Regulatory Activities (MedDRA) will be used to code AEs. AEs will be graded according to the National Cancer Institute CTCAE (Version 5.0).

The number of patients experiencing each AE will be summarised by the MedDRA system organ class and preferred term. The number and percentage of patients with AEs in different categories (eg, causally related, CTCAE Grade ≥ 3 etc) will be summarised, and events in each category will be further summarised by MedDRA system organ class and preferred term. SAEs will be summarised separately if a sufficient number occur.

Any AE occurring before the first dose of study drug will be included in the data listings but will not be included in the summary tables of AEs. AE summary tables will include only treatment-emergent adverse events. AEs will be defined as treatment emergent if they have an onset, or worsen (by investigator report of a change in intensity), during the study treatment period (defined from date of first dose of any study treatment to date of last dose of any study treatment) or safety follow-up period (28 days [± 7 days] after last dose of study treatment).

Any events in this period that occur after a patient has received further therapy for cancer (following discontinuation of IP) will be flagged in the data listings.

Discontinuation rate due to AEs will be summarised for the first 6 weeks and at any time.

During the evaluation of the AE data, an AstraZeneca medically qualified expert will review the list of AEs that were not reported as SAEs and AEs leading to discontinuation. Based on the expert's judgement, significant AEs of particular clinical importance may, after consultation with the Global Patient Safety Physician, be considered other significant adverse events and reported as such in the clinical study report. A similar review of laboratory/vital signs (pulse and BP)/ECG data will be performed for identification of other significant adverse events.

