2 DEFINITION OF ANALYSIS SETS

2.1 Study Design and Number of Patients

The study has a total of 4 dosing combinations:

- Osimertinib (80 mg od + savolitinib (300 mg od) (explored under Clinical Study Protocol [CSP] versions 1.0 to 4.0)
- Osimertinib (80 mg od) + savolitinib (300 mg bid) (explored under CSP versions 5.0 to 7.0)
- Osimertinib (80 mg od) + savolitinib (600 mg od) (explored under CSP versions 1.0 to 2.0 and reintroduced under CSP versions 5.0 to 6.0)
- Placebo to osimertinib + savolitinib (300 mg bid) (explored under CSP version 7.0)

The savolitinib 300 mg od [Once daily] regimen was originally sized to ensure there were sufficient patients in each of the diagnostic populations. Approximately **[CC1]** centrally confirmed Hepatocyte growth factor receptor [MET] Fluorescence in situ hybridisation+ [FISH+] patients were planned to be treated with osimertinib 80 mg od plus savolitinib 300 mg od. To achieve **[CC1]** centrally confirmed MET FISH+ patients at this dose, it was anticipated that **[CC1]** patients at this dose would be treated in this study, assuming **[CC1]** of these would be centrally confirmed FISH+ patients and **[CC1]** (**[CC1]** patients) would be centrally confirmed MET Immunohistochemistry+ [IHC+] patients. As the overall prevalence rates and the level of concordance between FISH and IHC methods may vary and a small number of patients recruited by pre-existing Next generation sequencing [NGS] may not have a central confirmation, it was anticipated that greater or less than **[CC1]** patients would be required to achieve **[CC1]** centrally confirmed MET FISH+ patients, however this was not expected to exceed **[CC1]** treated patients at this dose. If the proportion of patients who had central confirmation by IHC was lower than expected, additional patients were to be recruited to ensure there were at least **[CC1]** centrally confirmed MET IHC+ patients.

Under CSP version 5.0, approximately **[CC1]** patients (post First-line [1L] or Second-line [2L] osimertinib) were planned to be randomised in a 2:1 ratio to receive osimertinib 80 mg od in combination with either savolitinib 300 mg bid (approximately **[CC1]** patients) or savolitinib 600 mg od (approximately **[CC1]** patients). Since **[CC1]** patients had already received the 600 mg od dose (enrolled prior to CSP version 5.0,

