4 ANALYSIS METHODS

4.1 General principles

The below mentioned general analyses principles will be followed throughout the study:

- Statistical tests will be performed for two-sided hypothesis. All confidence intervals [CI] will use a 95% confidence level unless otherwise stated.
- Descriptive statistics will be used for all variables, as appropriate. Continuous variables will be summarised by the number of observations, mean, standard deviation [SD], median, quartiles (Q1 and Q3), minimum, and maximum. For log transformed data geometric mean [Geomean], geometric SD [gSD], geometric coefficient of variation [gCV%], median, minimum and maximum will be presented. Categorical variables will be summarised by frequency counts and percentages for each category.
- Unless otherwise stated, percentages will be calculated out of the analysis set total.
- Unless otherwise stated, for continuous data, mean, Geomean, median, quartiles as well as LSmeans will be rounded to 1 additional decimal place compared to the original data. The SD, gSD and standard error [SE] will be rounded to 2 additional decimal places compared to the original data. Minimum and maximum will be displayed with the same accuracy as the original data.
- For categorical data, percentages will be rounded to 1 decimal place.
- Ratio and CI of the ratio will be rounded to two decimal points
- P-values will be presented to three decimal points (displayed as “<0.001” for p-values lower than 0.001).
- SAS® version 9.4 (or higher) will be used for all analyses.
- There are two diagnostic populations of analytical interest as follows:
 - All Patients (FISH5+ and/or IHC50+): This population includes patients identified by lower MET biomarker cut offs (≥ 5 MET gene copies or MET:CEP7 ratio ≥ 2 [FISH5+] and/or $\geq 50\%$ of tumour cells staining at strong 3+ intensity [IHC50+])
 - FISH10+ and /or IHC90+: This population includes patients identified by higher MET biomarker cut offs (≥ 10 MET gene copies according to central MET FISH test [FISH10+] and/or $\geq 90\%$ of tumour cells staining at strong 3+ intensity according to central MET IHC test [IHC90+])

The populations are not mutually exclusive, i.e. a patient may be a member of both populations.

- Analyses will be presented by the assigned dosing regimen (i.e., savolitinib starting dose: 300 mg od, 300 mg bid and 600 mg od (in combination with osimertinib), or 300 mg bid + placebo.

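### SAP 4.2.3, Table 3 and 4.2.2.7.1 list combination-regimen safety, exposure and PK summaries only by MET cut-off, in conflict with the all-dosed safety set, so the denominators are ambiguous for patients without a central MET-positive result

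*SAP*

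**What the plan says.** **The set.** Protocol 9.3 defines the Safety Analysis Set (SAF) as "All enrolled patients who take ≥ 1 dose of either study drug". It adds: "The Safety Analysis Set (SAF) will be used as the population for reporting safety for patients dosed under all CSP versions". Protocol 9.4.4 repeats this: "The SAF will be used as the population for reporting safety for patients dosed under all CSP versions". None of these carries a MET condition. SAP 2.2 adopts the same definition and use, and assigns the PK analysis set to PK reporting under all protocol versions.

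**The safety lists.** SAP 4.2.3 begins "Unless otherwise stated, analysis of safety data will be based on SAF for patients dosed under all CSP versions as follows" and gives three groups. Two are combination groups, each with a MET cut-off. The wider of them reads "in combination with osimertinib in patients with EGFRm+, MET amplified/overexpressed (FISH5+ and/or IHC50+), locally advanced or metastatic NSCLC". The third is savolitinib monotherapy, with no cut-off stated.

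**SAP Table 3.** The combination rows for exposure and for safety carry the same two MET labels. The PK row carries FISH5+ and/or IHC50+ only, as does the bullet in SAP 4.2.2.7.1.

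**The label *All Patients*.** SAP 4.1 attaches it to FISH5+ and/or IHC50+: "This population includes patients identified by lower MET biomarker cut offs".

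**Entry to the study.** The footnote to Figure 1 in Protocol 1.3 describes FISH5+ and IHC50+ as central results and then says: "Under CSP versions 1-5, MET amplification as determined by pre-existing local NGS were also allowed". SAP 2.1 expects that "a small number of patients recruited by pre-existing Next generation sequencing [NGS] may not have a central confirmation".

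**The concern.** MET cut-offs select patients for efficacy. They give no reason to leave a dosed patient out of an adverse event rate, a laboratory or ECG summary, an exposure table or a concentration summary. If the bullets and Table 3 are programmed as written, no combination-regimen summary covers the whole SAF or the whole PK set. Any dosed patient without a central positive result is then missing from both numerator and denominator.

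Two programmers working from different SAP sections could produce different counts. The outputs affected include discontinuation due to adverse events and the hypersensitivity and hepatotoxicity tables. For uncommon events, one or two cases can change the reported rate.

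**Working it through.** **Step 1. Set the texts side by side.** There is no power, alpha or sample-size figure to reproduce.

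| Output | Text with a MET limit | Text without a MET limit |
|---|---|---|
| Adverse events | SAP 4.2.3 bullets; Table 3 safety row | Protocol 9.3, 9.4.4; SAP 2.2; SAP 4.2.3.2 (names the safety set) |
| Laboratory, ECG, vital signs | SAP 4.2.3 bullets; Table 3 safety row | Protocol 9.3, 9.4.4; SAP 2.2. SAP 4.2.3.4 to 4.2.3.6 name no population of their own |
| Exposure | Table 3 exposure row | SAP 4.2.3.1 (names the target population set and the SAF) |
| PK | Table 3 PK row; bullet in 4.2.2.7.1 | SAP 2.2. The 4.2.2.7.1 text on *All Patients* in the PK set is unclear, because 4.1 defines that label by cut-off |

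The conflict is therefore within the SAP as well as with the protocol.

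**Step 2. Trace one patient.** Take a patient enrolled on local NGS under versions 1 to 5, dosed, with central FISH and IHC either missing or negative.
- In the SAF? Yes, on one dose.
- In FISH5+ and/or IHC50+? Not if that means a central result, which is how Figure 1 and SAP 2.2 describe it.
- In FISH10+ and/or IHC90+? No. Those are stricter central cut-offs.
- In the monotherapy group? No. That arm exists only under version 7.0.

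The patient belongs to the SAF and to no listed combination group. SAP 3.2.5 does not settle the matter. For versions 1 to 6 it takes FISH5+/IHC50+ status from the testing used at enrolment, and it has no rule for someone whose enrolment test was NGS.

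**Step 3. See which regimens are open.** By the version history in SAP 2.1, versions 1 to 5 include patients on all three combination regimens. For 300 mg bid only version 5.0 patients can be affected, because versions 6.0 and 7.0 required central results. NGS-enrolled patients who were confirmed centrally are kept.

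**Step 4. Scale, by assumption only.** The number omitted, m, is not in the documents. For illustration take n = 193 retained. That is the number on 300 mg od with FISH5+ and/or IHC50+ and at least two scans (Protocol 2), and it is not the safety denominator.
- Share missing = m/(n+m).
- All-dosed rate when x events are seen among n: from x/(n+m) to (x+m)/(n+m). The upper end assumes that every omitted patient had the event.
- Chance of at least one event among those omitted = 1 − (1−p)^m.

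| m (assumed) | Share missing | All-dosed range when 4/193 = 2.1% is reported | Chance at p = 2% | at p = 3.7% | at p = 11.2% |
|---|---|---|---|---|---|
| 2 | 2/195 = 1.0% | 2.1% to 3.1% | 4% | 7% | 21% |
| 5 | 5/198 = 2.5% | 2.0% to 4.5% | 10% | 17% | 45% |
| 10 | 10/203 = 4.9% | 2.0% to 6.9% | 18% | 31% | 70% |

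The 2% is an assumed rate for an uncommon event. The 11.2% is hypersensitivity in an earlier phase I study at savolitinib 600 mg od (Protocol 2). The 3.7% is interstitial lung disease in the osimertinib pivotal studies (Protocol 2.3.1). Neither is a rate for this trial.

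**The case against.** The strongest reply is that the SAP already says otherwise. SAP 4.2.3 opens with an exception clause, 4.2.3.2 places the treatment-emergent event tables on the safety set, and 4.2.3.1 places exposure on the SAF, all without a MET limit. The PK bullet is garbled: it names 300 mg bid twice where Table 3 has 300 mg od, and words are missing. It is weak evidence of a deliberate restriction. The synopsis also describes patients before version 7.0 as FISH5+ and/or IHC50+, so the label may be loose shorthand for everyone enrolled. The remark about unconfirmed NGS patients is a planning assumption for the 300 mg od regimen, and no such patient is shown to exist. All adverse events and deaths are listed in any case.

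Much of this stands. A reader might infer that NGS-enrolled patients fall out of every combination summary. The documents do not support that, because several SAP sections allow a reading that keeps them. A reader might also infer an undeclared change of population, since SAP section 6 records none. That too depends on which text governs.

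The reply does not remove the conflict. SAP 4.2.3 also names the SAF and then says which parts of it are reported, so naming the SAF again in the subsections does not clearly override the bullets. The laboratory, ECG and vital-sign sections have no text of their own to fall back on. Figure 1 and SAP 2.1 show that the shorthand is not exact. Listings keep the cases visible but give no rates.

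**Conclusion.** The point holds as an unresolved conflict over denominators. Read literally, SAP 4.2.3, Table 3 and 4.2.2.7.1 give combination safety, exposure and PK summaries only for MET cut-off groups, against the all-dosed set in the protocol and in the SAP itself. Adverse event, laboratory, ECG, exposure and PK summaries may omit dosed patients who have no central FISH5+ or IHC50+ result.

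This rests on reading FISH5+/IHC50+ as central results, and on at least one dosed patient lacking them. The number is not given and is expected to be small, so the effect on any rate cannot be quantified. The table above shows scale under assumed counts and does not estimate bias. It would be tempting to read the 11.2% and 3.7% columns as probable losses in this trial, but those rates come from other studies and, for hypersensitivity, from a different regimen. If MET status is unrelated to toxicity, the expected rate is unchanged, and what is lost is precision and individual cases.

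The SAP should be corrected, because a literal reading departs from the protocol's safety population and the remedy is cheap.

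**What to change.** - In SAP 4.2.3 and the exposure and safety rows of Table 3, state that the main combination tables use the full SAF by regimen, with no MET condition.
- In 4.2.2.7.1 and the PK row of Table 3, state that PK summaries use the full PK analysis set by regimen, with no MET condition. Reconcile the regimen list in that bullet with Table 3.
- Keep the FISH5+/IHC50+ and FISH10+/IHC90+ tables as subsets.
- In 3.2.5 and 4.1, state how NGS-enrolled patients without a central positive result are classed.
- Reserve the label *All Patients* for all dosed patients, and give the cut-off population its own name.

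The cost is SAP wording and one further run of existing table programs, with no new data. If no dosed patient lies outside the cut-offs, the results do not change.
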